16.4 Adjusted Ideal Body Weight Calculation

MIRV dose will be based on AIBW.

Adjusted Ideal Body Weight (AIBW)
$$\text{AIBW} = \text{IBW}^1 + 0.4 (\text{Actual weight} - \text{IBW}^1)$$

Ideal Body Weight (IBW)
$$\text{IBW}^1 (\text{female}) = 0.9\text{H}^1 - 92$$

(¹H=height in cm; W=weight in kg)

16.5 RECIST 1.1 Criteria

Measurable disease: Measurable tumor lesions (nodal, subcutaneous, lung parenchyma, solid organ metastases) are defined as those that can be accurately measured in at least one dimension (longest diameter to be recorded) as ≥ 10 millimeter (mm) with CT scan or clinical examination. Bone lesions are considered measurable only if assessed by CT scan and have an identifiable soft tissue component that meets these requirements (soft tissue component ≥ 10 mm by CT scan). Malignant lymph nodes must be ≥ 15 mm in the short axis to be considered measurable; only the short axis will be measured and followed. All tumor measurements must be recorded in mm (or decimal fractions of cm). Previously irradiated lesions are not considered measurable unless progression has been documented in the lesion.

Malignant lymph nodes: pathological nodes must meet the criterion of a short axis of ≥ 15 mm by CT scan and only the short axis of these nodes will contribute to the baseline sum. All other pathological nodes (those with short axis ≥ 10 mm but < 15 mm) should be considered non-target lesions. Nodes that have a short axis < 10 mm are considered non-pathological and should not be recorded or followed.

Non-measurable disease: All other lesions (or sites of disease), including small lesions (longest diameter < 10 mm [< 1 cm] or pathological lymph nodes with ≥ 10 to < 15 mm [≥ 1 to < 1.5 cm] short axis), are considered non-measurable disease. Bone lesions without a measurable soft tissue component, leptomeningeal disease, ascites, pleural/pericardial effusions, lymphangitis cutis, inflammatory breast disease, lymphangitic involvement of lung or skin, and abdominal masses followed by clinical exam are all non-measurable. Lesions in previously irradiated areas are non-measurable unless progression has been demonstrated.

Note: Cystic lesions that meet the criteria for radiographically defined simple cysts should not be considered as malignant lesions (neither measurable nor non-measurable) since they are, by definition, simple cysts.

‘Cystic lesions’ thought to represent cystic metastases can be considered as measurable lesions, if they meet the definition of measurability described above. However, if non-cystic lesions are present in the same subject, these are preferred for selection as target lesions.

Target lesions: When more than one measurable tumor lesion is present at baseline all lesions up to a maximum of 5 lesions in total (and a maximum of 2 lesions per organ), representative of all involved organs, should be identified as **target lesions** and recorded and measured at baseline. Target lesions should be selected on the basis of their size (lesions with the longest diameter), be representative of all involved organs, but in addition should be those that lend themselves to reproducible repeated measurements. It may be the case that, on occasion, the largest lesion does not lend itself to reproducible measurement in which circumstance the next largest lesion which can be measured reproducibly should be selected. A sum of the diameters (longest for non-nodal lesions, short axis for nodal lesions) for all target lesions will be calculated and reported as the baseline sum diameters. If lymph nodes are to be included in the sum, then only the short axis is added into the sum. At baseline, the sum of the target lesions (longest diameter of tumor lesions plus short axis of lymph nodes: overall maximum of 5) is to be recorded.

After baseline, a value should be provided on the eCRF for all identified target lesions for each assessment, even if very small. If extremely small and faint lesions cannot be accurately

measured but are deemed to be present, a default value of 5 mm may be used. If lesions are too small to measure and indeed are believed to be absent, a default value of 0 mm may be used. The baseline sum diameters will be used as reference to further characterize any objective tumor regression in the measurable dimension of the disease.

Non-target lesions: All non-measurable lesions (or sites of disease) plus any measurable lesions over and above those listed as target lesions are considered **non-target lesions** and should also be recorded at baseline. Measurements of these lesions are not required, but the presence, absence, or in rare cases unequivocal progression of each should be noted throughout follow-up.

16.5.1 Evaluation of Response

Complete Response (CR): Disappearance of target and non-target lesions and normalization of tumor markers. Pathological lymph nodes must have short axis measures < 10 mm (Note: continue to record the measurement even if < 10 mm and considered CR). Residual lesions (other than nodes < 10 mm) thought to be non-malignant should be further investigated (by cytology, specialized imaging or other techniques as appropriate for individual cases) before CR can be accepted. Response should be confirmed in a subsequent scan \geq 4 weeks after the scan showing CR.

Partial Response (PR): At least a 30% decrease in the sum of the measures (longest diameters for tumor lesions and short axis measure for nodes) of target lesions, taking as reference the baseline sum of diameters. Non-target lesions must be non-progressive disease. Response should be confirmed in a subsequent scan \geq 4 weeks after the scan showing PR.

Stable Disease (SD): Neither sufficient shrinkage to qualify for PR nor sufficient increase to qualify for progressive disease, taking as reference the smallest sum diameters while on study. Documented at least once \geq 4 weeks from baseline.

Progressive Disease (PD): At least a 20% increase in the sum of diameters of measured lesions taking as references the smallest sum of diameters recorded on study (including baseline) AND an absolute increase of \geq 5 mm. Appearance of new lesions will also constitute progressive disease (including lesions in previously unassessed areas). In exceptional circumstances, unequivocal progression of non-target disease may be accepted as evidence of disease progression, where the overall tumor burden has increased sufficiently to merit discontinuation of treatment or where the tumor burden appears to have increased by at least 73% in volume. Modest increases in the size of one or more non-target lesions are NOT considered unequivocal progression. If the evidence of progressive disease is equivocal (target or non-target), treatment may continue until the next assessment, but if confirmed, the earlier date must be used.

An **Overall Response** assessment will be reported with **each protocol-specified timepoint** for a disease assessment. The following table provides a summary of the overall response status at each timepoint for subjects who have measurable disease at baseline.

Target Lesions	Non-target Lesions	New Lesions	Overall Response
CR	CR	No	CR
CR	Non-CR/non-PD	No	PR
CR	Not evaluated	No	PR
PR	Non-PD or not all evaluated	No	PR
SD	Non-PD or not all evaluated	No	SD
Not all evaluated	Non-PD	No	NE
PD	Any	Yes or No	PD
Any	PD	Yes or No	PD
Any	Any	Yes	PD

CR = complete response, PR = partial response, SD = stable disease, PD = progressive disease, NE = not evaluable

16.6 Grading of Ocular AEs [MIRV Cohort Only]

Table 15 Grading for Ocular Symptoms

Ocular AE	Grade 1	Grade 2	Grade 3	Grade 4
Blurred Vision A disorder characterized by visual perception of unclear or fuzzy images	Intervention not indicated	Symptomatic; limiting instrumental ADL ¹	Symptomatic; Limiting self-care ADL ²	Blindness in the affected eye
Dry Eyes A disorder characterized by dryness of the cornea and conjunctiva.	Asymptomatic; clinical or diagnostic observations only; symptoms relieved by lubricants	Symptomatic	Symptomatic; limiting self-care ADL ²	--
Eye Pain A disorder characterized by a sensation of marked discomfort in the eye.	Mild pain	Moderate pain; limiting instrumental ADL ¹	Severe pain; limiting self-care ADL ²	--
Floater A disorder characterized by an individual seeing spots before their eyes. The spots are shadows of opaque cell fragments in the vitreous humor or lens.	Symptomatic but not limiting ADL	Limiting instrumental ADL ¹	Limiting self-care ADL ²	--
Photophobia A disorder characterized by fear and avoidance of light.	Symptomatic but not limiting ADL	Limiting instrumental ADL ¹	Limiting self-care ADL ²	--

Abbreviations: ADL = activities of daily living

Table 16 Grading for Other Ocular Events

Ocular AE	Grade 1	Grade 2	Grade 3	Grade 4
Cataract A disorder characterized by partial or complete opacity of the crystalline lens of one or both eyes. This results in a decrease in visual acuity and eventual blindness if untreated.	Asymptomatic; clinical or diagnostic observation only; intervention not indicated	Symptomatic; glare symptoms affecting instrumental ADL ¹	Symptomatic limiting self-care ADL ²	Blindness in the affected eye
Conjunctivitis A disorder characterized by inflammation, swelling and redness to the conjunctiva of the eye.	Asymptomatic or mild symptoms; intervention not indicated	Symptomatic	Symptomatic; limiting self-care ADL ²	Blindness in the affected eye

Ocular AE	Grade 1	Grade 2	Grade 3	Grade 4
Decline in Best Corrected Visual Acuity (BCVA) (Vision Decreased) A disorder characterized by a decrease in visual acuity from baseline	--	Moderate decrease in visual acuity (BCVA 20/40 and better or 3 lines or less decreased vision from known baseline)	Marked decrease in visual acuity (BCVA worse than 20/40 or more than 3 lines of decreased vision from known baseline, up to 20/200)	BCVA worse than 20/200 in the affected eye
Extraocular muscle paresis A disorder characterized by incomplete paralysis of an extraocular muscle.	Asymptomatic; clinical or diagnostic observations only	Unilateral paresis without double vision	Bilateral paresis or unilateral paresis causing double vision in peripheral gaze, but not in central gaze	Bilateral paresis requiring head turning to see beyond central 60 degrees or double vision in central gaze
Eyelid Function Disorder A disorder characterized by impaired eyelid function.	Asymptomatic; clinical or diagnostic observations only; intervention not indicated	Symptomatic; non-operative intervention indicated; limiting instrumental ADL ¹	Limiting self-care ADL ² ; operative intervention indicated	--
Flashing lights A disorder characterized by a sudden or brief burst of light.	Symptomatic but not limiting ADL	Limiting instrumental ADL ¹	Limiting self-care ADL ²	--
Glaucoma A disorder characterized by an increase in pressure in the eyeball due to obstruction of the aqueous humor outflow.	Less than 8 mmHg of elevated intraocular pressure (EIOP); no visual field deficit	EIOP which can be reduced to 21 mmHg or under with topical medications and no visual field deficit	EIOP causing marked visual field deficits	Visual field deficit within the central 10 degrees of the visual field in the affected eye
Night blindness A disorder characterized by an inability to see clearly in dim light.	Symptomatic but not limiting ADL	Symptomatic; Limiting instrumental ADL ¹	Symptomatic; Limiting self-care ADL ²	Blindness in the affected eye
Papilledema A disorder characterized by swelling around the optic disc.	Asymptomatic; no visual field deficit	Symptomatic ³	Symptomatic ³	Blindness in the affected eye
Periorbital edema A disorder characterized by swelling due to an excessive accumulation of fluid around the orbits of the face.	Soft or non-pitting	Indurated or pitting edema; topical intervention indicated	Edema associated with visual disturbance; increased intraocular pressure, glaucoma or retinal hemorrhage; optic neuritis; diuretics indicated; operative	--

Ocular AE	Grade 1	Grade 2	Grade 3	Grade 4
			intervention indicated	
Retinal detachment A disorder characterized by fear and avoidance of light.	--	--	Macular sparing rhegmatogenous detachment	Macula-off rhegmatogenous retinal detachment
Retinal tear A disorder characterized by a small laceration of the retina, this occurs when the vitreous separates from the retina. Symptoms include flashes and floaters.	No retinal detachment and treatment not indicated	No retinal detachment and treatment indicated	--	--
Retinal vascular disorder A disorder characterized by pathological retinal blood vessels that adversely affects vision.	--	Retinal vascular disorder without neovascularization	Retinal vascular disorder with neovascularization	--
Retinopathy A disorder involving the retina.	Asymptomatic; clinical or diagnostic observations only	Symptomatic; limiting instrumental ADL ¹	Symptomatic; disabling; limiting self-care ADL ²	Blindness in the affected eye
Scleral disorder A disorder characterized by involvement of the sclera of the eye.	No change in vision from baseline	Symptomatic; limiting instrumental ADL ¹	Symptomatic; limiting self-care ADL ²	Blindness in the affected eye
Uveitis A disorder characterized by inflammation to the uvea of the eye.	Anterior uveitis with trace cells	Anterior uveitis with 1+ or 2+ cells	Anterior uveitis with 3+ or greater cells; intermediate posterior or pan-uveitis	Blindness in the affected eye
Vitreous hemorrhage A disorder characterized by bleeding into the vitreous humor.	Intervention not indicated	Symptomatic; limiting instrumental ADL ¹	Symptomatic; limiting self-care ADL ² ; vitrectomy indicated	Blindness in the affected eye
Watering eyes A disorder characterized by excessive tearing in the eyes; it can be caused by overproduction of tears or impaired drainage of the tear duct.	Intervention not indicated	Symptomatic ³	Symptomatic ³	Blindness in the affected eye
Eye Disorders - Other, specify	Asymptomatic or mild symptoms; clinical or	Moderate; minimal, local or non-invasive	Severe or medically-significant but not immediately sight-	Sight-threatening consequences; urgent

Ocular AE	Grade 1	Grade 2	Grade 3	Grade 4
	diagnostic observations only; intervention not indicated; no change in vision	intervention indicated; limiting instrumental ADL ¹	threatening; limiting self-care ADL ¹	intervention indicated; Blindness in the affected eye

Abbreviations: ADL = activities of daily living; BCVA = best corrected visual acuity; EIOP = elevated intraocular pressure

¹ Instrumental ADL: Ability to independently use a phone, do laundry, shop, prepare food, maintain housekeeping except occasional assistance, take own medications and manage finances.

² Self-Care ADL: Ability to independently bathe, dress, transfer, eat and perform personal toileting.

³ Per clinical practice and assessment of ophthalmologist or designee.

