3.5 Definition of Dose-Limiting Toxicity

Protocol-defined DLT criteria are applicable to the dose escalation portion of the study. The determinant period for DLT is the first cycle of treatment (i.e., 28 days for PLD cohorts, 21 days for MIRV cohorts); however, there is provision in the criteria below for AEs that occur beyond this period to be considered in the determination of the RP2D. All toxicities except for CRS and ocular AEs will be graded as per NCI CTCAE v5. CRS will be graded per the American Society for Transplantation and Cellular Therapy (ASTCT) Consensus Grading Criteria for CRS (described in Section 3.7.1.2); ocular AEs for the MIRV cohort will be graded per the tables provided in the Appendix Section 16.6. AEs clearly related to the underlying disease, disease progression, intercurrent illness, or concomitant medications are not considered DLTs. AEs that are clearly related to PLD or MIRV only do not have to be considered DLTs, unless the investigator considers the AE to be exacerbated by SL-172154. DLT is defined as an event considered related or possibly related to SL-172154 and meets one of the following criteria:

- Any death not clearly related to underlying disease or intercurrent illness
- Elevations in liver transaminases (aspartate aminotransferase [AST], alanine aminotransferase [ALT]) or total bilirubin:
 - In subject who enroll with AST/ALT/total bilirubin \leq upper limit of normal (ULN), AST or ALT elevation of $> 8x$ ULN **or** total bilirubin $> 5x$ ULN.
 - In subjects who enroll with AST/ALT/total bilirubin $>$ ULN, AST or ALT elevation of $> 8x$ baseline **or** total bilirubin $> 5x$ baseline.
 - Evidence of Hy's Law (AST or ALT $> 3x$ ULN [or baseline*] with concurrent increase in total bilirubin $> 2x$ ULN [*or baseline] without evidence of cholestasis or alternative explanation such as disease progression or viral hepatitis.

**ULN or baseline dependent on value at enrollment as described above.*

- Any AE that requires permanent discontinuation of SL-172154
- Any Grade 3 or greater AE except for those listed below:
 - Grade 3 fatigue lasting ≤ 7 days
 - Grade 3 anemia
 - Grade 3 or 4 neutropenia not associated with fever (temperature $> 38.5^{\circ}\text{C}$) that improves to Grade 2 within 7 days
 - Grade 3 or 4 lymphopenia
 - Grade 3 thrombocytopenia not associated with clinically significant bleeding and does not require medical intervention

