3.7.3.5 Ocular Disorders [MIRV Cohort]

Changes in visual acuity resulting from reversible keratopathy have been reported in other studies of DM4-containing immunoconjugates that use the SPDB linker [Younes, 2012]. Subjects receiving MIRV in the Phase 1 and 3 trials (IMGN853-0401, IMGN853-0403) reported ocular AEs consistent with reversible keratopathy/corneal epitheliopathy. At the 6.0 mg/kg AIBW Q3W dose level, MIRV-related dry eye (26% all grades; 1% Grade ≥ 3), keratopathy (33% all grades; 1% Grade ≥ 3), blurred vision (42% all grades; 2% Grade ≥ 3), eye pain (13% all grades; 1% Grade ≥ 3), and photophobia (12% all grades; 1% Grade ≥ 3) were reported in Phase 3 study IMGN853-0403.

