Recommended dosage modifications for corneal AEs should be based on both corneal examination findings using the system outlined in [Table 8](#) and changes in BCVA. Dose modifications for non-corneal ocular AEs are at the discretion of the treating physician, in collaboration with an eye care professional.

Note: [Table 8](#) describes the management of corneal adverse reactions with regard to MIRV dosing. See [Table 15](#) and [Table 16](#) in Appendix Section [16.6](#) for grading of ocular AEs.

Table 8 Management of Corneal Adverse Reactions (Keratitis/Keratopathy)

Ocular Exam Finding ^a	Management	Guidelines for MIRV Dose Modification
Nonconfluent superficial keratitis or nonconfluent keratopathy ^b	Complete eye examination as outlined in SOA (Section 6.2). Subjects should have frequent symptomatic ocular assessments and repeat eye examinations at least every 6 weeks until resolved to pretreatment baseline or nonconfluent superficial keratitis or better or are deemed to be irreversible by the investigator, even after treatment discontinuation, if needed	Monitor with scheduled ocular exam to complete resolution or return to pretreatment baseline. Continue MIRV dosing.
Confluent superficial keratitis or confluent keratopathy ^b , cornea epithelial defect (+NaFl staining), or \geq 3-line loss in BCVA	Complete eye examination as outlined in SOA (Section 6.2). Subjects should have weekly symptomatic ocular assessments and repeat eye examinations at least every 6 weeks until resolved to pretreatment baseline or are deemed to be irreversible by the investigator, even after treatment discontinuation, if needed.	Hold MIRV dosing until AE has resolved to pretreatment baseline or nonconfluent superficial keratitis or better. Subjects with corneal adverse reactions lasting $<$ 14 days may be allowed to resume MIRV at the same dose level. Recurrence of toxicity on subsequent cycles despite best supportive care will require a dose reduction to one lower dose level. Subjects with corneal adverse reactions lasting \geq 14 days but no more than 28 days may resume MIRV at one lower dose level. If findings persist $>$ 28 days, continuation at reduced dose level is at the discretion of the investigator in consultation with the Sponsor.

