Corneal ulcer or clinically significant stromal opacity or BCVA 20/200 or worse	Complete eye examination as outlined in SOA (Section 6.2). Subjects should have weekly symptomatic ocular assessments and repeat eye examinations at least	Hold MIRV dosing. Subjects may be allowed to resume MIRV at one lower dose level after AE has resolved to

Ocular Exam Finding ^a	Management	Guidelines for MIRV Dose Modification
	every 6 weeks until resolved to baseline or are deemed to be irreversible by the investigator, even after treatment discontinuation, if needed.	nonconfluent keratitis or better or to pretreatment baseline within 28 days. If findings persist >28 days, continuation at reduced dose level is at the discretion of the investigator in consultation with the Sponsor.
Corneal perforation	Complete eye examination as outlined in SOA (Section 6.2). Subjects should have weekly symptomatic ocular assessments and repeat eye examinations at least every 6 weeks until resolved to baseline or are deemed to be irreversible by the investigator, even after treatment discontinuation, if needed.	Permanently discontinue MIRV dosing.

^a Normal = clear cornea, no epithelial defects.

^b Nonconfluent microcystic epithelial change, punctate epithelial keratopathy, subepithelial inclusion cyst and/or nonconfluent superficial keratitis, superficial punctate keratitis, epithelial erosion

Table 9 Management of Ocular Disorders

Refer to [Table 8](#) for Corneal Adverse Reactions.

Severity Grade (CTCAE v5.0)	Management	Guidelines for MIRV Dose Modifications
Grade 1	Follow SOA (Section 6.2) Monitor for worsening symptoms	Continue MIRV dosing
Grade 2	Complete eye exam as outlined in SOA (Section 6.2) Repeat complete exam as clinically indicated. Subjects should have weekly symptomatic ocular assessments by the investigator until the symptoms resolve to Grade \leq 1 or are deemed to be irreversible by the investigator.	Hold MIRV dosing until AE has resolved to Grade 1 or better. Subjects with ocular symptoms lasting < 14 days may be allowed to resume MIRV at the same dose level. Subjects with ocular symptoms lasting \geq 14 days but no more than 28 days may resume MIRV at one lower dose level. Recurrence of Grade 2 toxicity on subsequent cycles despite best supportive care will require a MIRV dose reduction of one dose level.

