5.3.2.2.2 Lubricating Artificial Tears

Subjects assigned to receive MIRV will be mandated to use lubricating artificial tears on a daily basis (as directed by the product prescribing information or the treating physician). Preservative-free lubricating drops are recommended. Subjects should be advised to wait at least 15 minutes after corticosteroid eye drop administration before instilling lubricating eye drops.

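### The dry-eye Grade 1 and Grade 2 definitions in Appendix 16.6 overlap for symptoms relieved by lubricants, and keratopathy has no grade definition of its own there

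*Protocol*

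**What the plan says.** Protocol Section 3.5 states that "ocular AEs for the MIRV cohort will be graded per the tables provided in the Appendix Section 16.6"; Sections 3.7 and 9.2.4 say the same. All other toxicities except CRS are graded by CTCAE v5.

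**Dry eye.** Table 15 gives Grade 1 as "Asymptomatic; clinical or diagnostic observations only; symptoms relieved by lubricants". Grade 2 is the one word for symptomatic, with no qualifier or footnote. Grade 3 adds a limit on self-care. Section 5.3.2.2.2 adds that "Subjects assigned to receive MIRV will be mandated to use lubricating artificial tears on a daily basis". Table 9 continues MIRV at Grade 1; at Grade 2 it says "Hold MIRV dosing until AE has resolved to Grade 1 or better".

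**Cornea.** Section 3.7.3.5 reports that subjects in earlier MIRV trials "reported ocular AEs consistent with reversible keratopathy/corneal epitheliopathy". Table 8 sorts corneal reactions by examination finding, one tier being "Confluent superficial keratitis or confluent keratopathy", and sets MIRV dosing from the finding. The note above Table 8 sends the reader to Tables 15 and 16 for the grade. Neither table has a row for keratitis, keratopathy, epithelial defect or corneal ulcer. The row left is "Eye Disorders - Other, specify", at the end of Table 16.

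**The concern.** A severity scale should give one grade for one clinical picture. For dry eye this one does not: a relieved but symptomatic eye can be recorded as Grade 1 at one site and Grade 2 at another, each following the text. Because the drops that relieve symptoms are compulsory, this picture should not be rare.

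The stakes are reported severity and treatment guidance. Incidence and severity of AEs is a primary outcome (Section 2). Grade above 1 also triggers a complete eye examination (Section 3.7.3.5.1), a hold of MIRV until that examination (Section 3.7.3.5.2), and the Table 9 split.

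For the cornea the issue is narrower. The reader is sent to tables that do not name the event, and must use a row built on symptoms, daily activities, need for intervention and vision. Two eyes in different Table 8 tiers may get the same grade, and one eye may be graded differently by two raters.

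**Working it through.** This is a reading of definitions; the plan gives no figure to reproduce. The arithmetic at the end only sets the scale.

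**1. Dry eye, case by case (Table 15).**

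| Clinical picture | Grade 1 cell | Grade 2 cell | Result |
|---|---|---|---|
| No symptoms, finding on examination only | met | not met | Grade 1 |
| Symptoms, relieved by lubricants, self-care not limited | last clause met, first clause not | met | 1 or 2 |
| Symptoms, not relieved, self-care not limited | not met | met | Grade 2 |
| Symptoms limiting self-care | – | – | Grade 3 |

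Only the second line is ambiguous. If the Grade 1 clauses must all hold, the cell contradicts itself, since it requires both no symptoms and relieved symptoms. If they are alternatives, the cell overlaps Grade 2. A rule that the higher grade wins would leave the lubricant clause without use; a rule that the more specific clause wins gives Grade 1. The plan states neither.

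**2. What the Grade 1/2 line changes.**
- Reporting: the maximum-grade tables (SAP Table 14.3.1.5 and the MIRV-related version of 14.3.1.7).
- Conduct: the examination at emergence, the hold until examination, and Table 9.
- Not the SAP table of MIRV-related Grade 3 or 4 ocular events (14.3.1.24b), because dry-eye Grade 3 has its own self-care anchor.

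**3. Which scale.** Table 9 heads its grade column CTCAE v5.0, and Sections 3.7.3.5.1 and 3.7.3.5.2 speak of CTCAE grades for ocular events. Section 3.5 exempts ocular AEs from CTCAE. A site cannot tell from the text whether the Table 15 grade is the one that enters Table 9.

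**4. Cornea, row by row.** Table 15 has five rows: blurred vision, dry eyes, eye pain, floaters, photophobia. Table 16 has 18 named rows, cataract to watering eyes, then the generic row. None is corneal. A corneal event with vision loss can also be graded on the visual-acuity (BCVA) row; without vision loss, the generic row is what remains.

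Table 8's tiers cannot simply be copied in as Grades 1 to 4, because they cross the BCVA row:
- Second tier: loss of 3 lines or more. BCVA row: more than 3 lines is already Grade 3.
- Third tier: 20/200 or worse. BCVA row: worse than 20/200 is Grade 4.

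**5. Scale.** Inputs from Section 3.7.3.5 (single-agent Phase 3, all grades): "MIRV-related dry eye (26% all grades"; keratopathy 33%, second only to blurred vision at 42%. Cohort sizes from Section 3.3.2: 64 in expansion, 70 planned, and 70 + 10 = 80 if the optional subjects are added. Expected count = N × rate.

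| N | Dry eye (0.26 × N) | Keratopathy (0.33 × N) |
|---|---|---|
| 64 | 16.6 | 21.1 |
| 70 | 18.2 | 23.1 |
| 80 | 20.8 | 26.4 |

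The Grade 3-or-greater rate is 1% for each event, so about 0.01 × 70 = 0.7 subjects.

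**The case against.** The other side has several good points.

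- **Keratopathy can be graded.** A reader might infer from the missing row that it has no grade. The generic row supplies Grades 1 to 4 for any unlisted eye event, and the BCVA row covers vision loss. This stands: what is missing is a specific definition.
- **Corneal dosing does not depend on grade.** Section 3.7.3.5.2 bases it on corneal findings and BCVA. This stands, so a reader should not conclude that the missing row alters corneal dosing.
- **Dry-eye guidance is soft.** Section 3.7.3.5.2 leaves non-corneal ocular dose changes to the physician with the eye care professional, and Section 3.7 calls the guidelines non-prescriptive. Nor does Grade 2 by itself lead to a lasting reduction: Table 9 allows the same dose if symptoms last under 14 days, and a lower level enters with longer duration or recurrence. This limits the consequence but does not remove the overlap; the severity record is affected whatever the dosing decision.
- **The specific clause should prevail.** Giving the lubricant clause precedence is sensible, but the text does not say so.
- **Papilledema and watering eyes.** Their Grade 2 and 3 cells are worded alike, and a reader might list them as the same defect. Footnote 3 assigns that split to the ophthalmologist or designee, so the documents do not support it.

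**Conclusion.** The dry-eye overlap is a real drafting defect, confined to symptoms relieved by lubricants. It affects reported Grade 1 versus Grade 2 severity and the guidance attached to that line. It does not reach the SAP Grade 3 or 4 ocular table.

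The corneal point is secondary. The second most frequent ocular event listed in Section 3.7.3.5 is graded on a generic row with no stated link to Table 8. This bears on severity reporting and on the Grade 3-or-greater DLT criterion. Its reach on DLTs is narrow, because Section 3.5 does not require events clearly due to MIRV alone to be counted.

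About 18 and 23 of 70 subjects are upper bounds. They assume that single-agent rates carry over to the combination, and they count every dry-eye or keratopathy event, including those that any rater would grade alike. One subject may have both, so the two should not be added. The documents give no basis for the share that is truly ambiguous.

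**What to change.** 1. In Table 15, make dry-eye Grades 1 and 2 mutually exclusive by placing symptoms relieved by lubricants in one cell only. Which cell is the sponsor's decision.
2. Reconcile Table 15 with Table 9 and Sections 3.7.3.5.1 and 3.7.3.5.2, which cite CTCAE grades, so that one scale is named for ocular AEs throughout.
3. Have the sponsor state in Appendix 16.6 how corneal events are graded, and reconcile that definition with Table 8 and the BCVA row. This review chooses neither the clinical anchors nor any dosing rule.

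The cost is appendix wording, a site memo and some regrading. Corneal events can draw on eye examinations, though routine ones fall only at baseline, before Cycles 3, 5 and 7, and at the post-treatment visit. Dry-eye regrading may be incomplete, since the protocol does not say that relief by lubricants is recorded. Section 16.7 says the ocular tables were added to align with other MIRV protocols, so changing them gives up some comparability. If the sponsor regrades, showing the grades as first recorded beside the revised ones would keep that loss visible.
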